	Principal Investigator Name/Contact Info:	[name] MD. [name] [name]. [name] MD, PHD [name] MD [contact]
	Primary Contact Name/Contact Info	[name] MD. [contact]
	Date Revised:	
	Study Number:	

patients will be randomized using computer generated tables and sealed envelopes. A designated resident not involved in the study will open the sealed envelope and randomize the patient into the following groups:

Group A—Liposomal bupivacaine(133mg bupivacaine diluted normal saline total 25cc)

Group B---Dexamethasone 4mg in 0.5% Bupivacaine 25cc

The patients will be transferred to the OR to proceed with the surgery. Standard ASA monitors will be placed again and after pre oxygenation, general anesthesia will be induced with propofol and fentanyl. Laryngeal mask airway of appropriate size will be inserted and patient will be connected to the ventilator for the procedure. Maintenance of anesthesia will be achieved with sevoflurane and oxygen/air mixture. Once the procedure is completed, patients will be extubated and transferred to the recovery room(PACU) for post anesthetic care.

The patient will also receive 4mg of ondansetron intra-venous in the OR as prophylaxis for post operative nausea and vomiting.

Patients, attending anesthesiologists, surgeon and research assistant collecting the data will be blinded of the group assignment. The medication solution will be prepared by the resident physician.

 Mount Sinai	Protocol Title:	COMPARISON OF THE ANALGESIC EFFICACY OF A SINGLE SHOT INTERSCALENE BLOCK WITH LIPOSOMAL BUPIVACAINE TO BUPIVACAINE WITH DEXAMETHASONE AS AN ADJUVANT-A RANDOMIZED CONTROLLED TRIAL
	Principal Investigator Name/Contact Info:	[name] MD. [name] [name]. [name] MD, PHD [name] MD [contact]
	Primary Contact Name/Contact Info	[name] MD. [contact]
	Date Revised:	
	Study Number:	

Pain scores in the form of NRS (NUMERICAL RATING SCALE) will be assessed on arrival to PACU. Pain scores will also be assessed 1 hour after arrival to PACU and at the time of discharge from PACU. NRS scores will be assessed on the floors every 6 hourly during the first 24 hours, 8 hourly and then every 12 hourly during the second 24 hours. If NRS scores are more than 5 at any time a one-time dose of oxycodone 10mg and Tylenol 1000 mg will be given.

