Once the primary team discharges the patient, a telephone follow - up every day until resolution of any residual arm weakness/numbness will be done by the anesthesia resident originally involved in the surgery.

Patients will also be asked to note the time to first analgesic request in addition to onset of sensory discomfort and motor recovery.

a) Recruitment Methods

See above. With the HIPAA waiver requested, the surgeon will provide investigators (both of whom are physicians within the department of Anesthesiology) with information of eligible patients. After the operating room schedule has been reviewed for potential participants in the study the contact information will be obtained through the surgeon's office. Subjects will be called by the department of Anesthesiology when their surgery is scheduled, and they will be informed about the study then.

 Mount Sinai	Protocol Title:	COMPARISON OF THE ANALGESIC EFFICACY OF A SINGLE SHOT INTERSCALENE BLOCK WITH LIPOSOMAL BUPIVACAINE TO BUPIVACAINE WITH DEXAMETHASONE AS AN ADJUVANT-A RANDOMIZED CONTROLLED TRIAL
	Principal Investigator Name/Contact Info:	[name] MD. [name] [name]. [name] MD, PHD [name] MD [contact]
	Primary Contact Name/Contact Info	[name] MD. [contact]
	Date Revised:	
	Study Number:	

b) Inclusion and Exclusion Criteria

Inclusion criteria: All patients between age 18-75 years undergoing primary shoulder arthroscopic procedure. All patients who speak read and understand English will be included for follow up purposes.

Exclusion criteria included patients with patient refusal, ASA 5, presence of coagulopathy, severe lung disease, contralateral diaphragmatic palsy, insulin-dependent diabetes, hepatic disease/failure, kidney disease/failure, pregnancy, chronic opioid use (defined as opioid use for >3 months), or allergy to any of the study medications.

c) Number of Subjects

N= 100, recruit ability is manageable. Based on previous study conducted by Tandoc et al with estimated average duration of analgesia at 22 hours with dexamethasone in 0.5% bupivacaine and assumed average SD of 3 hours, they estimated that 16 patients would be needed to provide 80% power to conclude absence of effect at the significance level of 0.05 among treatment groups. To allow for 20% patient dropouts, 30 subjects per group will be targeted for enrollment.

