Data will be expressed as mean \pm SD or median with interquartile range as appropriate. Categorical data will be analyzed with Fisher exact test and chi-square test. The duration of analgesia and motor block will be analyzed by the Kaplan-Meier survival analysis and Cox

 Mount Sinai	Protocol Title:	COMPARISON OF THE ANALGESIC EFFICACY OF A SINGLE SHOT INTERSCALENE BLOCK WITH LIPOSOMAL BUPIVACAINE TO BUPIVACAINE WITH DEXAMETHASONE AS AN ADJUVANT-A RANDOMIZED CONTROLLED TRIAL
	Principal Investigator Name/Contact Info:	[name] MD. [name] [name]. [name] MD, PHD [name] MD [contact]
	Primary Contact Name/Contact Info	[name] MD. [contact]
	Date Revised:	
	Study Number:	

proportional hazards modeling. Subgroup pairwise analyses will be conducted via Kruskal-Wallis rank test with Bonferroni correction for significance. All analysis will be conducted with intent-to-treat approach to minimize the potential effects of dropout. Statistical significance will be defined as $P<0.05$.

d) Study Timelines

2018-2019 and subsequent data analysis. The subject's participation will be from time of enrollment to complete resolution of arm weakness and motor strength. Estimated date of enrollment completion will be when 100 eligible subjects are enrolled in final data analysis. Estimate date for study completion will be June 2019.

e) Study Endpoints

Primary end point will be the time of first analgesic request for the first 24 hours post operatively.

Secondary end points will be NRS at 6 hours, 12 hours, 18 hours, 24 hours, 36 hours and 48 hours and oxycodone use.

f) Procedures Involved in the Human Research

Prospective randomized controlled trial and data analysis only.
Ultrasound guided interscalene block with nerve catheter placement.

 Mount Sinai	Protocol Title:	COMPARISON OF THE ANALGESIC EFFICACY OF A SINGLE SHOT INTERSCALENE BLOCK WITH LIPOSOMAL BUPIVACAINE TO BUPIVACAINE WITH DEXAMETHASONE AS AN ADJUVANT-A RANDOMIZED CONTROLLED TRIAL
	Principal Investigator Name/Contact Info:	[name] MD. [name] [name]. [name] MD, PHD [name] MD [contact]
	Primary Contact Name/Contact Info	[name] MD. [contact]
	Date Revised:	
	Study Number:	

g) Specimen Banking

N/A

h) Data Management and Confidentiality

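### The plan's only multiplicity correction is attached to pairwise subgroup tests that a two-arm trial does not have, while the several primary outcomes get none

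*Combined protocol and SAP*

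**What the plan says.** Section 5 (Study Design) describes the allocation step, "A designated resident not involved in the study will open the sealed envelope and randomize the patient into the following groups", and lists two groups only: "Group A—Liposomal bupivacaine(133mg bupivacaine diluted normal saline total 25cc") and "Group B---Dexamethasone 4mg in 0.5% Bupivacaine 25cc".

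The statistical paragraph closes section 5(c), Number of Subjects. It assigns categorical data to Fisher and chi-square tests. For durations it says "The duration of analgesia and motor block will be analyzed by the Kaplan-Meier survival analysis and Cox" modeling. The next sentence is "Subgroup pairwise analyses will be conducted via Kruskal-Wallis rank test with Bonferroni correction for significance". It does not say which subgroups, which outcome or how many comparisons are meant. The paragraph ends with a general significance level of 0.05. No test is named for the arm comparison of NRS or opioid use, unless the Kruskal-Wallis sentence is meant to serve.

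On outcomes, section 1 (Objectives) names analgesia duration and motor recovery as primary. Still under the primary label, it adds time to first analgesic request, NRS at 6, 12, 24 and 48 hours and on postoperative days 3 to 7, and total narcotic consumption. Section 5(e) (Study Endpoints) instead gives a single primary end point, time to first analgesic request within 24 hours, and makes NRS and oxycodone use secondary.

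**The concern.** Pairwise testing with Bonferroni belongs to a design with three or more groups, where an overall test is followed by several between-group comparisons. This trial has one comparison to make, so the correction has no work to do.

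If patient subgroups were meant, the sentence cannot be carried out as written, because the divisor would be chosen after the data are seen. A rank test within each subgroup would also not show whether the treatment effect differs between subgroups.

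The multiplicity that does exist, across the outcomes labelled primary in section 1, is left open. At stake is what a single P value below 0.05 would mean. Without a rule, a result on any one of the listed outcomes could be presented as the trial's primary finding.

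**Working it through.** **1. Between-arm pairs.** With g = 2 groups the number of pairs is g(g − 1)/2 = 1. Bonferroni gives 0.05/1 = 0.05, so the threshold is unchanged.

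**2. Outcomes under the primary label in section 1.** Analgesia duration (1), motor recovery (1), time to first request (1), NRS at 6, 12, 24 and 48 h and on days 3, 4, 5, 6 and 7 (9), total narcotic use (1). Total: 13.

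**3. Chance of at least one false positive.** Each outcome is tested at 0.05, no true differences are assumed, and the outcomes are taken as independent: 1 − 0.95^k.

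| Outcomes treated as primary | k | Result |
|---|---|---|
| Single end point in section 5(e) | 1 | 5.0% |
| Two named durations in section 1 | 2 | 1 − 0.9025 = 9.8% |
| Everything under the label in section 1 | 13 | 1 − 0.5133 = 48.7% |

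These outcomes are related, and analgesia duration and time to first request nearly coincide, so the true figures would be lower. For two test statistics that are jointly normal with an assumed correlation of 0.5 or 0.8, the 9.8% becomes 9.1% or 7.8%.

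**4. The plan's own sample-size figure.** Section 5(c) gives "assumed average SD of 3 hours, they estimated that 16 patients would be needed to provide 80% power" but no difference to detect. With an assumed difference of 3 h, two-sided 0.05 and 80% power, n per group = 2(1.960 + 0.842)² × 3²/3² = 15.7, which rounds up to 16. The stated 16 is therefore matched, per group, if 3 h is assumed, and 3 h is used below for that reason. It is not a figure from the documents.

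**5. Cost of correcting two primaries.** SD 3 h and 30 per group are from section 5(c); the difference is assumed. The standardized signal is δ/(σ√(2/n)) = 3/(3 × √(2/30)) = 3.873.

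- At 0.05, normal approximation: Φ(3.873 − 1.960) = 97.2%; with the noncentral t distribution, 96.8%.
- At 0.025, normal approximation: Φ(3.873 − 2.241) = 94.9%; with the noncentral t distribution, 93.9%.

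At an assumed 2 h difference the signal is 2.582, and the normal approximation gives Φ(0.622) = 73.3% falling to Φ(0.341) = 63.3%. If all 13 stayed primary, the Bonferroni level would be 0.05/13 = 0.0038. Power at 3 h would then be 83.7% by the normal approximation, or 80.0% by noncentral t. These are two-sample mean comparisons, used as a guide to the time-to-event tests. Holm costs no more than Bonferroni.

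**The case against.** The best defence is that the sentence does little harm. Durations are already assigned to Kaplan-Meier and Cox. For two groups Kruskal-Wallis is the two-sided rank-sum test (identical P values, 0.00887, in a numerical check), so it is a valid test for fully observed outcomes such as NRS. It may even be what the plan intends for them. Bonferroni over one pair costs no power, and Bonferroni never inflates error. All of this stands. It leaves the sentence undefined and the primary outcomes uncorrected.

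It can also be said that section 5(e) has a single primary end point, or that both durations might be required to succeed. Either would remove the inflation, but section 1 contradicts the first and nothing states the second.

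Two stronger readings are tempting and are not supported.

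- **That Kruskal-Wallis would be run on censored durations, losing power or inflating error.** The sentence follows the one on durations but does not refer to them. Simulation used normal durations with mean 22 h and SD 3 h, 30 per arm unless stated. The one censoring source the plan supplies, the 24 h window, did no material harm: type I error was 5.7% (5.2% with 50 per arm), and power at 3 h was 93.3% against 92.2% for log-rank. Harm appeared only when early dropout times, assumed uniform over 0 to 24 h, were also ranked as if analgesia had ended. With 20% dropout in each arm, power at 3 h was 61.4% against 86.1% for log-rank, with type I error at 5.3%. With 10% against 30% dropout, type I error was 19.9%, or 32.2% with 50 per arm. The documents state neither that ranking rule nor unequal dropout; the 20% in section 5(c) is only an enrollment allowance.
- **That tests in two to four subgroups carry a 10% to 19% false-positive risk.** That is the value without correction, and the sentence specifies Bonferroni. With it, 1 − (1 − 0.05/k)^k is 4.9% for k = 2, 3 and 4.

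**Conclusion.** The point holds as a misplaced and undefined correction. The only multiplicity adjustment in the text available has one between-arm pair to act on and no defined subgroups. The outcomes labelled primary in section 1 have no adjustment.

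If success on any one outcome would count, the false-positive chance is 9.8% for the two named durations and up to 49% for all 13. Both figures assume independent outcomes and no true effect; correlation lowers them. If the single end point in section 5(e) governs, the chance is 5%, so the size of the problem depends on a conflict that the protocol has to settle. No claim is made that the planned duration analysis itself is invalid.

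**What to change.** 1. Delete the sentence on pairwise subgroup analyses.
2. Keep Kaplan-Meier and Cox for durations and name the log-rank test as the comparison. Name the Wilcoxon rank-sum test for NRS and opioid totals.
3. If a subgroup is of interest, define it in advance and examine it by a treatment-by-subgroup interaction in the Cox model.
4. Reconcile the primary outcomes in section 1 with the end point in section 5(e). State whether success needs one or all of the outcomes kept as primary. If one is enough, apply Holm or Bonferroni across them.

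This changes wording only, with no new data or procedures. The statistical cost depends on how many primaries remain. With one there is none. With two it is about 3 percentage points of power at an assumed 3 h difference and 30 per arm, but about 10 points at 2 h, which argues for a short primary list.

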	Date Revised:	
	Study Number:	

Based on the above two options in the current opioid epidemic crisis, we propose to study the analgesic efficacy of liposomal bupivacaine to bupivacaine with dexamethasone as an adjuvant in interscalene block for shoulder surgeries. Till date, there is not study comparing the two.

1) Objectives:

Research Question:

Is the analgesic efficacy of liposomal bupivacaine superior to that of bupivacaine with dexamethasone as an adjuvant in interscalene block?

Primary Outcome: The primary outcomes is the time of analgesia duration (defined as the onset of sensory discomfort that required medication) and time of motor recovery (defined as the recovery of full motor function of both wrist and elbow on the nerve block side). Time to first analgesic request, NRS at 6 hours, 12 hours, 24 hours and 48 hours, POD 3, 4, 5, 6, 7 and total narcotic consumption.

Secondary Outcome: arm weakness (0 to 24 hours, 24 to 48 hours), arm numbness (0 to 24 hours, 24 to 48 hours), nausea, vomiting, dizziness, Horner's syndrome, hoarseness, dyspnea, Intra operative narcotic consumption, PACU and hospital length of stay, pain scores as assessed by PT on POD 1, and 2.

 Mount Sinai	Protocol Title:	COMPARISON OF THE ANALGESIC EFFICACY OF A SINGLE SHOT INTERSCALENE BLOCK WITH LIPOSOMAL BUPIVACAINE TO BUPIVACAINE WITH DEXAMETHASONE AS AN ADJUVANT-A RANDOMIZED CONTROLLED TRIAL
	Principal Investigator Name/Contact Info:	[name] MD. [name] [name]. [name] MD, PHD [name] MD [contact]
	Primary Contact Name/Contact Info	[name] MD. [contact]
	Date Revised:	
	Study Number:	

patient's satisfaction scores(Yes- I would prefer the same analgesic technique the next time or No-I would prefer a different analgesic technique) and quality of sleep (good, moderate/average, bad) on POD 0 and 1. Patient reported outcomes measurement information system (PROMIS) baseline global assessment will be conducted prior to surgery and post operative pain assessment at first follow up visit. Each patient will be assessed by standardized assessment of shoulder function as recommended by American association of shoulder and elbow surgery.

2) Background

See above. There have been several studies demonstrating efficacy of dexamethasone in prolonging the analgesic effect when administered both perineurally and intra-venously as an adjuvant to local anesthesia demonstrating a dose effect relationship.

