Data collected in excel file to be de-identified after initial collection. Excel file be subsequently encrypted and shared only between the two above listed investigators via secure Mt. Sinai (chpnet) electronic mail.

The information included in the data will be medical record number, age, gender, ASA class, type of surgery, pain score assessments, duration of surgery, anesthesia time, time to first narcotic, total narcotic use and pain scores up to 48 hours after surgery. In case of known history of type 1 or 2 diabetes, preoperative and post operative finger stick will be recorded. Time of administration of study drug, smoking status and patient satisfaction scores will also be recorded. Only the research personnel will have access to the data. The data will be stored as a hard copy files and on a secure spreadsheet. The research personnel are responsible for the receipt of the data. The PI will keep the hard copies secure and any electronic data will be encrypted. No personal identifiers will be used. The data will undergo statistical analysis.

i) Provisions to Monitor the Data to Ensure the Safety of subjects

 Mount Sinai	Protocol Title:	COMPARISON OF THE ANALGESIC EFFICACY OF A SINGLE SHOT INTERSCALENE BLOCK WITH LIPOSOMAL BUPIVACAINE TO BUPIVACAINE WITH DEXAMETHASONE AS AN ADJUVANT-A RANDOMIZED CONTROLLED TRIAL
	Principal Investigator Name/Contact Info:	[name] MD. [name] [name]. [name] MD, PHD [name] MD [contact]
	Primary Contact Name/Contact Info	[name] MD. [contact]
	Date Revised:	
	Study Number:	

Part I: Elements of Data and Safety Monitoring Plan

MSSM Principal Monitor:

Last Name: [name]

First Name: [name]

Academic Title: Attending Physician, Professor

Department: Anesthesiology

Mailing Address: Mount Sinai West [name]

[contact]

Fax:

E-mail: [contact]

MSSM Principal Monitor:

Last Name: [name]

First Name: [name]

Academic Title: Attending Physician, Assistant Professor

Department: Anesthesiology

Mailing Address: Mount Sinai West [name]

[contact]

Fax:

E-mail: [contact]

Last Name: [name]

First Name: [name]

Academic Title: Attending Physician, Professor

Department: Orthopedics

Mailing Address: Mount Sinai West [name]

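### Participation and post-discharge calls stop when the block resolves, which conflicts with the plan's fixed 48 h and day 7 assessments and can give the arms unequal opioid and pain follow-up

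*Combined protocol and SAP*

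**What the plan says.** All references are to the combined protocol and SAP.

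**End of follow-up.** Section 5(d), Study Timelines: "The subject's participation will be from time of enrollment to complete resolution of arm weakness and motor strength". Section 5, Study Design, provides that after discharge "a telephone follow - up every day until resolution of any residual arm weakness/numbness will be done". Neither sets a minimum period of contact. Section 1 lists time of motor recovery among the primary outcomes, so the event that ends participation is close to an outcome of the trial.

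**Data required at fixed times.**
- Section 1, under primary outcome: "NRS at 6 hours, 12 hours, 24 hours and 48 hours, POD 3, 4, 5, 6, 7 and total narcotic consumption". The narcotic total has no window.
- Section 5(e): "Secondary end points will be NRS at 6 hours, 12 hours, 18 hours, 24 hours, 36 hours and 48 hours and oxycodone use". Oxycodone use has no clear window either.
- Section 5(h), list of data fields: "time to first narcotic, total narcotic use and pain scores up to 48 hours after surgery". The 48 h may govern narcotic use as well as pain scores; the wording allows both readings.
- Section 5 also has an NRS schedule over two days, but for patients on the floors.

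**First analgesic request.** Section 5(e): "Primary end point will be the time of first analgesic request for the first 24 hours post operatively". Section 5: "Patients will also be asked to note the time to first analgesic request in addition to onset of sensory discomfort and motor recovery". Section 1 lists analgesia duration and first request with no time limit.

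**Analysis.** Section 5(c) assigns duration of analgesia and of motor block to Kaplan-Meier and Cox methods and gives no censoring rule.

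**The concern.** The two arms are compared because their blocks may last for different times. If contact ends when the block ends, the length of observation is itself affected by treatment. Pain and opioid use would be expected to rise as the block wears off, so observation may stop about when the outcome begins, and at different clock times in the two arms.

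Two kinds of outcome are at stake. The first is total narcotic or oxycodone use and the later NRS scores, which would be summed or sampled over unequal time. The second is time-to-event outcomes without a time limit. If patients were censored at block resolution, and sensory and motor offset are correlated, that censoring would be informative. Opioid sparing is part of the trial's stated motivation. Data not collected after discharge cannot be reliably recovered at analysis, and the intention-to-treat statement in 5(c) does not replace them.

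**Working it through.** **1. What the plan supplies.** It gives no time to motor or sensory resolution, no discharge time, no call times and no opioid rate. The only related figure is in 5(c): mean analgesia duration of 22 h with dexamethasone, SD 3 h. If that is borrowed as a proxy for resolution, P(resolved by 24 h) = Φ((24 − 22)/3) = Φ(0.67) = 0.75. This shows only that resolution before the 36 h and 48 h assessments is plausible.

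**2. Opioid model.** Let B be the shorter-acting and A the longer-acting arm. Analgesia ends at T, Normal(22, 3) in B and Normal(22 + d, 3) in A. The rate is r_b during the block and r_a after it. Weakness and numbness resolve at T + lag.

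Assumed, not in the documents:
- d = 3, 12 or 24 h
- (r_b, r_a) = (0, 10 mg/6 h), (10 mg/24 h, 10 mg/6 h) or (10 mg/24 h, 10 mg/12 h)
- lag = 0 or 6 h
- calls at multiples of 24 h after the block
- nothing recorded after the last observation

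This makes 3 × 3 × 2 = 18 scenarios. Two rules have a closed form for the mean difference A − B:
- Stop at resolution: r_b × d. With r_b = 10/24 mg/h this is 1.25, 5.0 and 10.0 mg; with r_b = 0 it is 0.
- Fixed 48 h, when blocks end before 48 h: −(r_a − r_b) × d. With (0, 10/6) this is −5.0 mg at d = 3 and −20.0 mg at d = 12. At d = 24 some blocks outlast 48 h, and simulation gives −39.2 mg instead of −40.

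Simulation with 400,000 patients per arm gives these ranges over the three rate pairs (A − B, mg):

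| Opioid counted to | Lag | d = 3 | d = 12 | d = 24 |
|---|---|---|---|---|
| resolution | 0 or 6 h | 0 to +1.25 | 0 to +5.0 | 0 to +10.0 |
| next daily call | 0 h | +6.3 to +11.4 | +9.9 to +14.9 | 0 to +10.0 |
| next daily call | 6 h | −1.7 to +0.4 | −16.2 to −3.1 | 0 to +10.0 |
| fixed 48 h | either | −5.0 to −1.2 | −20.0 to −5.0 | −39.2 to −9.8 |

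Over the fixed window A uses less in every scenario. Counted to the next daily call, A appears to use more in 11 of 18, the same in 2 and less in 5.

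**3. Equal lag and spread in both arms.** Take first request at 22 h in B and 30 h in A, resolution 2 h later on average (24 and 32 h), SD 3 throughout, correlation 0.6, and 10 mg per 6 h from first request (all assumed except 22 h and SD 3). Use over 0–48 h is (48 − 22) × 10/6 = 43.3 mg in B and (48 − 30) × 10/6 = 30.0 mg in A.
- Counted to resolution: 3.9 mg in each arm, so the difference disappears.
- Counted to the next daily call: 23.4 mg in B and 29.9 mg in A, so the sign reverses. Half of B has its last call at 24 h; almost all of A is called at 48 h.

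**4. First analgesic request.** Take requests at Normal(22, 3), with motor recovery on average 3 h before, at, or 3 h after the request (SD of the gap 3 h, assumed).
- Observation stopped exactly at recovery: 84%, 50% and 16% of requests are missed.
- Last daily call at or after recovery: 16%, 7.5% and 1.8% are missed, all later than 24 h. None within 24 h is lost, because that call is at 24 h or later.

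For the outcome with no time limit, suppose patients were censored exactly at resolution, with mean resolution 20 h (SD 3) and true median request 22 h. The Kaplan-Meier median becomes 22.8, 24.0 and 26.0 h at correlation 0.3, 0.6 and 0.8. With mean resolution 26 h it stays at 22.0–22.1 h.

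**The case against.** The best defence is that the plan does contain fixed windows. Section 5(h) can be read as 48 h for narcotic use, 5(e) sets NRS to 48 h, and section 1 sets NRS to day 7 and an assessment at the first follow-up visit. Taken literally, 5(d) would rule out much of that, so it may be loose wording. This stands in part: a reader might infer that the sponsor chose block resolution as the outcome window, and the documents do not support that. They show a conflict. But a list of data fields is not a contact schedule, and nothing says how a discharged, recovered patient is reached at 36 h, 48 h or day 7.

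Second, a reader might infer that the 24 h first-request end point is biased. It is not, to any important extent. It has a fixed limit, patients note the time themselves, and a daily call at or after recovery picks up requests in the first 24 h. A small gap could remain because 5(e) counts from surgery while the check counts from the block.

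Third, a reader might infer that the longer-acting arm is necessarily penalised. It is not: with a 6 h lag and d = 12 h the direction is right, only diluted. The repeated 10 mg doses are also an assumption, since section 5 describes a one-time dose.

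Fourth, censoring at resolution is an inference; 5(c) states no rule. And 22 h (SD 3) describes analgesia, so it cannot be reported as 75% of an arm leaving the study by 24 h.

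**Conclusion.** The point holds as an unreconciled conflict with a real consequence. Followed as written, 5(d) and the call rule in section 5 end contact on a treatment-dependent event, before assessments that other sections require. For discharged patients this gives unequal collection of opioid use and later NRS by arm.

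The opioid comparison can be biased and, under some assumptions, reversed: 11 of the 18 scenarios when counting to the next daily call. Those results rest on assumed opioid rates, call times, lags and arm differences, and on patients being followed by calls alone. They show that the problem can be large; they are not an estimate of it. Of the time-to-event outcomes, those exposed are analgesia duration and first request as listed in section 1, without a time limit.

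Severity: should-fix.

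**What to change.** - **Sections 5(d) and 5 (post-discharge calls).** Separate the end of follow-up from block resolution. Contact every randomised patient, in hospital or at home, on the same fixed schedule through at least 48 h after the block, regardless of arm recovery. Continue through postoperative day 7 if the day 3–7 NRS scores are kept. Calls go on longer only for residual weakness or numbness.
- **Sections 1, 5(e) and 5(h).** Define total narcotic consumption as all opioid taken from 0 to 48 h after the block in every patient. Use the same NRS times in all three places.
- **Section 5(c).** State that block resolution is not a censoring event for analgesia duration or first request.

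**Cost.** Protocol wording, plus one or two short calls for patients whose block resolves early, made by the resident who already calls. Keeping the day 3–7 scores adds up to five more contacts per patient (days 3, 4, 5, 6 and 7). No new procedures are needed.
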